## **18. DISSEMINATION OF FINDINGS**

Findings of this feasibility study will be disseminated to a range of stakeholders, including researchers, clinicians, individuals with IC, and students. At least 1 paper will be submitted to international peer-reviewed journals (i.e. Circulation and European Heart Journal). Also at least 1 abstract will be submitted to international conferences. We will hold a stakeholder event at the end of the project as a method for guiding best practice for researchers. Glasgow Caledonian University is rated No. 1 in Scotland for physiotherapy education, and this research will be used to inform undergraduate and postgraduate modules on clinical research. The project will also form part of a PhD thesis at the Glasgow Caledonian University.

Patients with symptomatic PAD should receive the same secondary prevention management as patients with symptomatic coronary artery disease. Improving daily physical activity (PA) is particularly important in individuals with IC as lower PA levels have been recognised as a strong predictor of increased morbidity and mortality in this population.³ Current NICE guidelines recommend the use of supervised exercise programmes (SEPs), encouraging patients “to exercise to the point of maximal pain”, as first line treatment.⁴ However, while systematic reviews (e.g.⁵) show that SEPs lead to a significant improvement in the absolute walking distances of patients with IC on a treadmill, it is unclear if this is sustained or leads to improvement in daily PA.⁵ Furthermore, due to the considerable resources required to deliver the recommended 3 months exercise programme (30-45 minutes 3x weekly), SEPs are not always routinely available to NHS patients, and time and travel costs tend to lead to low patient uptake and high attrition rates.⁶ Therefore, investigating the feasibility of using low-cost, patient-centred interventions that can support increased PA is warranted.

Lack of self-efficacy, attributed to poor understanding of the disease and uncertainty regarding the importance of exercise, has been shown to be a major barrier to exercise uptake in patients with PAD and IC.⁷ Educating patients with IC about their disease pathology and the benefits of walking is key to enhancing success of secondary prevention strategies for people with IC.^{7,8} We recently piloted a structured, patient-centred education intervention (SEDRIC)⁹ with the specific aim of educating patients with IC about their condition, improving patient ownership, and promoting self-managed walking. In addition to improved treadmill walking distances, we found out that there was a trend for patients to increase their daily PA.

For patients with IC to gain benefits of secondary prevention, exercising beyond the point when pain occurs is recommended, representing another barrier to engagement in PA.¹⁰ Despite this, our systematic review¹¹ found that pain management as a route to facilitate exercise and PA has rarely been explored. Recent interest has focused on the use of TENS (a low-cost, non-invasive pain management device) to improve angiogenesis, muscle function,¹² pain and walking distances in patients with IC.^{13,14} TENS has a strong placebo effect in pain conditions,¹⁵ and testing effectiveness against placebo is advocated. In a proof-of-concept pilot study, we demonstrated that TENS could significantly improve pain and increase treadmill walking distances above placebo levels.¹⁴ Our exploratory study also established that home use of TENS was both acceptable and provided self-reported improvement in PA in individuals with IC.¹⁶

Although patient-centred education (SEDRIC) and TENS have both demonstrated potential to improve daily PA in people with IC, the use of these components in combination has not previously been evaluated. We therefore propose a 2 x 2 (TENS versus placebo TENS x SEDRIC versus no additional education) feasibility RCT¹⁷ that will compare use of TENS against placebo TENS with and without a patient-centred education programme.

Aims: To determine the feasibility of Transcutaneous Electrical Nerve Stimulation device used within or without a patient centred education programme to improve walking distances in patients with PAD.

General Research Questions:

What is the feasibility (i.e. recruitment and retention rates, adherence, safety, sample size for a definitive trial, potential for effectiveness) of conducting a definitive RCT comparing TENS with and without patient-centred education?

How acceptable are TENS and patient-centred education as interventions on their own or in combination in patients with IC?

Specific Objectives:

To estimate rates of recruitment, retention, intervention uptake and adherence, and outcome completion for a definitive RCT.

To monitor, record, manage and follow-up specified adverse events in all groups.

To collect and synthesise data, including walking outcomes, physical activity and patient reported outcomes, PROMs, from which the sample size of a definitive RCT could be estimated.

To explore participants' experiences and perceptions of the interventions and trial procedures via focus groups.

SECTION 3: STUDY METHODS

Trial design:

We will conduct a 2 x 2 parallel group (TENS versus placebo TENS x SEDRIC versus no additional education) feasibility RCT to compare use of TENS against placebo TENS with and without a patient-centred education programme. Permuted block randomisation will be implemented to allocate patients to trial arms. The intervention will last for 6 weeks, and patients recruited within the first eight months will be further followed up for 3 months. Outcomes assessments will be implemented at baseline, after six weeks treatment and at 3 months follow up. We will collect information regarding the recruitment rate, intervention uptake, outcome measure completion rate, attrition rate, blinding fidelity, efficacy related to the primary, secondary and other PROMs, and patients experience of intervention including acceptability and ease of intervention.

Randomisation:

A central randomisation facility (interactive voice response system, IVRS) will allocate the randomised therapy per patient. The IVRS, based at the Data Centre, will be available by telephone. Stratified permuted block randomization procedures will be utilised to allocate patients to groups (Patients allocation will be stratified by gender and age, ABPI values). Permuted block design (PBD) will be used to allocated patients to the PE+TENS, PE+Placebo TENS, TENS, Placebo TENS using 4-way randomisation throughout the whole time until the recruitment of a minimum of 20 subjects in the each of the larger comparison groups are achieved.

Sample size:

Details regarding sample size calculation can be found in section 8.7 of the full study protocol (version 2.0). Summarily, 16 participants per group will allow detection of an effect size of 1.0sd of ACD in active TENS group compared to placebo control. Allowing for 20% attrition, we will recruit 20 participants in each group, and therefore aim to recruit 80 patients.

Framework

The superiority comparison will be implemented to compare change in physical activity and PROMs between treatment groups (PE+TENS, PE+Placebo TENS, TENS) versus Placebo TENS. Also superiority comparison will be implemented for within treatment groups from baseline. A non-superiority comparison shall be made between the PE+TENS group versus each of the PE+Placebo TENS, TENS groups. The feasibility, acceptability (the recruitment, retention, outcome completion, intervention uptake and attrition rates, and patient tens feedback) and adverse events data will be summarised by randomised group and overall using descriptive statistics. No formal statistical tests comparing the randomised groups will be pre-specified. Framework analysis will be implemented for the qualitative focus group data.

Statistical analysis and stopping guidance

Interim analysis will not be conducted, and the study will stop at last patient last study visit. All outcomes will be analysed collectively at the end of the study. P-value will be set at $p < 0.05$.

Timing of outcome assessments

Physical activity and PROMs outcomes will be assessed at baseline, end of six weeks intervention (up to 2 weeks window), and 3 months post-randomisation (up to 2 weeks window). The recruitment, retention, outcome completion, intervention uptake and attrition rates will be assessed at the end of the study. Blinding and patients acceptability of TENS and

ease of use will be assessed at the point of patient exit from the study. Further assessment regarding patients' qualitative experience of intervention will be done at 3 months post-randomisation (up to 2 weeks window).

SECTION 4: STATISTICAL PRINCIPLES

Level of confidence interval and p-values

Analysis will be conducted at 95% CI, and 0.05 level of significance.

Adherence and Protocol Deviations:

Patient adherence to the intervention will be defined, as applicable, by patients attendance at the education session, and answering to at least one of the 2-weekly phone calls, and/or using TENS at least 30 mins per day 3x/wkly for at least 50% of the 6 weeks of intervention. Specifically, the TENS log (questionnaire) as well as inbuilt record of TENS device usage will both be used to analyse patients utilisation of TENS. Researcher adherence to intervention protocol will be defined as implementation of intervention and outcome assessment according to the approved study protocol.

Protocol deviation will be defined as accidental or unintentional changes to, or non-compliance with the research protocol that does not increase risk or decrease benefit or; does not have a significant effect on the subject's rights, safety or welfare; and/or on the integrity of the data. We will document deviations due to rescheduled study (If they fall outside the specified window), failure to complete a physical activity outcome assessment or self-report questionnaire, patients' refusal to complete scheduled research activities. Details regarding level (major or minor) number and type of protocol deviations per group will be summarised in addition to potential impact on analysis populations.

Analysis populations

Comparisons will be undertaken to investigate the feasibility of studying the proposed outcomes for definitive trial and to calculate estimates for the likely effect sizes and 95% confidence intervals, even though determining differences in clinical outcomes is not the primary purpose of this feasibility trial. Inferential analysis will be implemented using the principles of intention-to-treat.

SECTION 5: STUDY POPULATION

Screening, Eligibility and Recruitment Data:

The number of potential participants screened, eligible and the number recruited will be analysed and presented in a CONSORT flow diagram. Data regarding level of withdrawal from intervention and/or follow up as well as timing of withdrawal/lost to follow up will be analysed. In addition, data descriptive of reasons and details patterns of withdrawal/lost to follow up will be presented.

Baseline patient characteristics

The following patient baseline characteristics will be summarised: Age, gender, ABPI score, Diagnosis of APD, Diagnosis of IC, Past medical history, Cardiac risk factors, Present drug history. Also selected outcome measures including, ICD, ACD, McGill and VAS pain scores, SF-36 and ICQ OoL scores, Geriatric depression questionnaire, Pain self-efficacy questionnaire, and Brief illness perception questionnaire scores will be presented as baseline characteristics. Categorical data will be presented using counts and percentages. Continuous data will be presented using number of patients, mean (SD), median (min-max), and IQR.

SECTION 6: ANALYSIS

Outcome definitions

Feasibility and acceptability outcomes:

Measure recruitment rates -reasons for non-eligibility and non-recruitment of eligible patients will be recorded via the study screening log
Measure participant's retention throughout the trial and reasons for withdrawal
Monitor, record, manage and follow-up defined adverse events in all groups
Measure uptake of intervention (log of TENS use and attendance at education) and acceptability of these interventions via a questionnaire
Measure blinding fidelity via TENS feedback questionnaire
Outcome completion rate – number of day activPAL is worn at each outcome time point.

Efficacy outcomes

Measurement will be obtained at baseline, following six weeks intervention and at 3 months follow up

Primary efficacy outcomes

Treadmill assessed Absolute Claudication Distance (ACD) (cm).

Secondary efficacy outcomes will include:

Physical activity capacity secondary outcomes

Treadmill assessed Initial Claudication Distance (ICD), assessed by a treadmill exercise using the Gardner treadmill protocol.¹⁹ Measurement will be obtained at baseline, following six weeks intervention and at 3 months follow.

Daily physical activity. We shall specify 3 days activPAL data at each measure as minimum for including patient activPAL data in the efficacy analysis. However, activPAL were time (number of day worn) will be also be reported as part of the feasibility analysis. For secondary efficacy analysis, activPAL data outcomes: total number of **i**) steps; **ii**) upright events; **iii**) walking events; **iv**) Event-based claudication index (ratio of walking events to upright events) participants undertake in a day.²⁰

PROM secondary outcomes

Disease specific quality of life will be as assessed using the Intermittent Claudication Questionnaire (ICQ).

Generic quality of life via the SF-36;

Pain quality will be recorded using the McGill Pain Questionnaire (MPQ) 5 minutes after every treadmill test.

Average Pain intensity in the past 7 days will be recorded using a Visual Analogue Scale

Illness beliefs and psychosocial determinants of health and behaviour will be recorded using the Illness Perception Questionnaire (IPQ), Geriatric Depression Scale (Short Form) (GDS-SF) and the Pain Self-Efficacy Questionnaire (PSEQ).

Qualitative Experience outcome

Analysis Methods

Feasibility and qualitative data analysis

Descriptive statistics will be used to characterize the groups at baseline and to present the feasibility outcomes.

Outcomes related to experience and perception via focus groups will be analysed by framework analysis.

To determine the feasibility of conducting a definitive trial, descriptive statistics will be used to report the number and proportion of participants who meet the inclusion criteria, who consented to participating, and who dropped out during the trial. Also descriptive analysis will report compliance with intervention by recording participants' attendance to education session, follow up calls, attendance to TENS training session, (rate of use of TENS) rate of outcome measure completion, and total accelerometer wear time. Specifically, the TENS log (questionnaire) as well as inbuilt record of TENS device usage will both be used to analyse patients utilisation of TENS. Acceptability of TENS will be obtained by TENS feedback questionnaire

Further exploration will be carried out to determine factors that impact on propensity to participate looking at the difference in characteristics between participants and non-participants. If less than 10% of the individuals with PAD/IC in the clinic are eligible to participate, or if less than 10% of eligible patients agreed to participate, then the eligibility criteria and recruitment strategy will be adjusted prior to conducting a definitive trial. Adjustment of the recruitment strategy in a definitive trial will be made comparing the difference in the baseline characteristics between participants and non-participants. Similarly, association between participants' baseline characteristics and trial outcome will also inform decision on adjustment of recruitment strategy and stratification factors in the definitive trial. Data collection for the definitive trial will be adjusted based on the information related to type, quantity of missing data, and the mechanisms by which these data are missing.

The transcripts from the focus group discussions will be analysed using framework analysis. The data gathered from the exit interview will form part of acceptability analysis and be used to adapt the intervention to enhance its acceptability in a definitive trial.

Primary efficacy analysis

Differences in the change in ACD will be analysed and effect scores calculated using Chi-squared tests, Mann-Whitney U or Wilcoxon signed-rank tests as applicable for between and within-group comparisons and log-rank method for pooled samples or sub-strata. Baseline participants' variability will be controlled for using the analysis of co-variance.

Secondary efficacy analysis

Differences in the changes in activPAL outcomes, ICD, SF-36 and ICQ scores, MPQ score, IPQ, GDS-SF, PSEQ, ABI, and Biomarkers will also be analysed and effect scores calculated using Chi-squared tests, Mann-Whitney U or Wilcoxon signed-rank tests as applicable for between and within-group comparisons and log-rank method for pooled samples.

Safety analysis

The safety data (adverse events)- both numbers of subjects and events – will be summarised by randomised group and overall using descriptive statistics. No formal statistical tests comparing the randomised groups will be pre-specified.

Software for statistical analysis

The statistical software to be used is either SAS 9.2 for Windows, Cary, NC, USA or SPSS Version 22.

PrEPAID Statistical Analysis Plan (Version 1.0)
 Approval date:

Table 1: Participant characteristics at baseline

	PE+TENS	PE+ Placebo TENS	TENS	Placebo TENS
Age				
Sex (%male)				
Ankle-brachial index				
Diagnosis of PAD				
Date of diagnosis:				
\geq 3months <6months				
\geq 6months<12months				
\geq 12months				
Type of PAD				
Iliac				
Femoral				
Popliteal				
Other				
Diagnosis of IC				
Date of diagnosis:				
\geq 3months <6months				
\geq 6months<12months				
\geq 12months				
Limb affected				
Left				

PrEPAID Statistical Analysis Plan (Version 1.0)

Approval date:

Right				
Both				
Fontaine Classification				
I				
II				
III				
IV				
Past Medical History				
IHD: Y/N				
MI: Y/N				
LVH: Y/N				
Cardiac risk factors				
DM : Y/N				
Family History of IHD/CVA/ BP: Y/N				
Hypercholesterolemia: Y/N				
Hypertension: Y/N				
Alcohol excess:				
Current				
Previous				

PrEPAID Statistical Analysis Plan (Version 1.0)

Approval date:

Never				
Smoking:				
Current				
Previous				
Non-smoker				
Present drug history:				
Statin Y/N				
Antiplatelet Y/N				
Anticoagulant Y/N				
Outcome measures				
Treadmill maximal walking distance				
Treadmill pain free walking distance				
Daily steps				
Pain intensity(VAS)				
McGill pain score				
QoL SF-36 score				
ICQ score				
Geriatric depression questionnaire score				
Pain self-efficacy questionnaire score				
Brief illness perception questionnaire				

Table 2: Feasibility related outcome tables

Participants recruitment					
Total number of participants screened(n)					
Total number of eligible participants (n/%)					
Reasons for non-eligibility					
X (n/%)	Whole study sample	PE+TENS	PE+ Placebo TENS	TENS	Placebo TENS
Recruitment target/Number recruited.					
Recruitment rate (n/centre/month)					
Outcome completion rate					
Reasons for withdrawal from intervention					
Retention rate (proportion of participants with valid primary outcome data at 3-months follow-up)					
Retention rate (proportion of participants with valid ActivPAL outcome data at 3-months follow-up)					
Reason for withdrawal from follow up					
Timing of withdrawal					
Intervention uptake and Adherence rate					
Attendance to PE					
Summary from phone calls					
TENS log summary					
Objective record of TENS use					
Acceptability of intervention					
Acceptability questionnaire					
Adverse events rate					
List them					
TENS blinding					

PrEPAID Statistical Analysis Plan (Version 1.0)
 Approval date:

Table 3: Changes in groups' outcomes at 6-wweks compared to placebo (usual care alone)

	TENS	PE+TENS	PE
ACD	$x \pm sd$ vs $x \pm sd$; $p=xxx(95\%cl)$		
ICD			
Daily steps			
Upright events			
Walking events			
EBCD			
ICQ			
SF-36			
7-day Average pain intensity			
Pain quality			
IPQ			
GDS-SF			
PSEQ			

*Also compare between PE+TENS and each of TENSs and PE alone (May not present in a table)

PrEPAID Statistical Analysis Plan (Version 1.0)
 Approval date:

Table 4: Changes in groups' outcomes at 3 months compared to placebo (usual care alone)

	TENS	PE+TENS	PE
ACD	$x \pm sd$ vs $x \pm sd$; $p=xxx(95\%cl)$		
ICD			
Daily steps			
Upright events			
Walking events			
EBCD			
ICQ			
SF-36			
7-day Average pain intensity			
Pain quality			
IPQ			
GDS-SF			
PSEQ			

*Also compare between PE+TENS and each of TENSs and PE alone ((May not present in a table)

Table 5: Within group comparisons between baseline and after 6 weeks intervention and 3 months follow up

	TENS	PE+TENS	PE	Usual care alone
ACD Post 6 wks Post 3 months follow up	$x \pm sd$ vs $x \pm sd$; $p = xxx$ (95%cl)			
ICD Post 6 wks Post 3 months follow up				
Daily steps Post 6 wks Post 3 months follow up				
Upright events Post 6 wks Post 3 months follow up				
Walking events Post 6 wks Post 3 months follow up				
EBCD Post 6 wks Post 3 months follow up				
ICQ Post 6 wks Post 3 months follow up				
SF-36 Post 6 wks Post 3 months follow up				
7-day mean pain intensity Post 6 wks Post 3 months follow up				
Pain quality				

PrEPAID Statistical Analysis Plan (Version 1.0)
Approval date:

Post 6 wks Post 3 months follow up				
IPQ Post 6 wks Post 3 months follow up				
GDS-SF Post 6 wks Post 3 months follow up				
PSEQ Post 6 wks Post 3 months follow up

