Methodology:	This a randomised controlled feasibility trial using a 2x2 factorial design of TENS versus placebo TENS with or without patient-centred education. Participants will be blinded to the type of TENS they receive. Outcome assessment of the primary outcome will be done by a blinded assessor.
Sample Size:	80
Screening:	Participants will be screened for eligibility by Research Nurse
Registration/Randomisation:	Randomisation by Robertson Centre for Biostatistics
Main Inclusion Criteria:	
 
• Clinical diagnosis of symptomatic Peripheral Arterial Disease (PAD) including resting ABPI <0.9 in at least one leg
 

	
 
• Stable IC for <math>\geq 3</math> months
 
• Walking limited primarily by claudication
 
• Able to exercise on a treadmill
 
• Able to read and speak English to a level allowing satisfactory completion of the study procedures
 
• Able to provide written informed consent for participation
 

Main Exclusion Criteria:	
 
• Planned surgical or endovascular intervention for PAD within the next 3 months
 
• Critical limb ischaemia
 
• The presence of any absolute contraindications to exercise testing/training as defined by the American College of Sports Medicine (ACSM)
 
• Previous experience of using TENS/ structured patient education for PAD
 
• Contraindications to TENS (including epilepsy, dermatological conditions, indwelling electrical pumps/pacemakers) and inability to apply TENS independently.
 
• Patients who require walking aids including artificial limbs
 
• Major surgery, myocardial infarction or stroke/ TIA in the previous 6 months
 
• Co-morbidities that cause pain or limit walking to a greater extent than IC (e.g. severe arthritis)
 
• <math>>20\%</math> variation in baseline ACD on treadmill
 
• Severe peripheral neuropathies above the ankle.
 
• Participation in another research protocol
 
• Participants <math>< 40</math> years of age
 

Product, Dose, Modes of Administration:	One-off 3 hours structured patient education + twice weekly phone call follow up to six weeks; High frequency TENS for daily use up to six weeks; placebo TENS for daily use for six weeks
Duration of Treatment:	Six weeks

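### The 2x2 trial plans all four simple effects, but no TENS or education main effect and no interaction with an adjusted 95% CI

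*SAP*

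**What the plan says.** The Methodology row of the protocol synopsis describes a trial "using a 2x2 factorial design of TENS versus placebo TENS with or without patient-centred education". SAP Section 3 (Trial design) names the same two factors but calls the design a 2 x 2 parallel group trial.

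SAP Section 3 (Framework) lists the comparisons:

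- Superiority comparisons to "compare change in physical activity and PROMs between treatment groups (PE+TENS, PE+Placebo TENS, TENS) versus Placebo TENS", plus change from baseline within groups.
- "A non-superiority comparison shall be made between the PE+TENS group versus each of the PE+Placebo TENS, TENS groups". No margin, direction or decision rule is given.

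The Framework sentence names physical activity and PROMs, but the table shells apply the same structure to ACD, their first row. Table 3 covers "outcomes at 6-wweks compared to placebo (usual care alone") and has columns for TENS, PE+TENS and PE (patient education); Table 4 repeats it at 3 months. A footnote to both reads "Also compare between PE+TENS and each of TENSs and PE alone (May not present in a table"). Table 5, titled "Within group comparisons between baseline and after 6 weeks intervention and 3 months follow up", shows all four arms.

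Two phrases hint at pooling. Recruitment is to continue until there are "a minimum of 20 subjects in the each of the larger comparison groups" (SAP Section 3, Randomisation), and the primary efficacy analysis includes a "log-rank method for pooled samples or sub-strata" (SAP Section 6). The same paragraph plans an analysis of covariance to control for baseline variability, without listing treatment terms.

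**The concern.** A 2x2 layout lets every patient contribute to the estimate of each factor. The plan never takes up that option. No TENS effect averaged over education, no education effect averaged over TENS, no interaction and no model with factor terms appears in either document. The two hints of pooling do not fill the gap: what is pooled is not stated, and a log-rank method does not give a mean difference in ACD.

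This matters because the SAP says that the comparisons should yield effect sizes with 95% CIs (Section 4, Analysis populations), and that the data should allow a definitive trial to be sized (Specific Objectives). A team planning that trial would want the factor effects and some idea of the interaction, estimated by a rule fixed in advance.

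The comparisons of the combination with each component have a separate, smaller problem. The non-superiority label does not say what would be tested or concluded, and their place in the tables is left open.

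**Working it through.** **Inputs.** Protocol 8.7: two-sided 5% level, 80% power, difference of 1.0 SD of ACD, 16 per group, 20% attrition, 20 per group, 80 in total. SAP Section 3: four arms. Assumed here: equal arms, a common SD set to 1, and full 20% attrition (16 evaluable per arm, 64 in all).

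**1. The plan's own figure.** n = 2(1.960 + 0.842)²/1.0² = 15.7, so 16 per group, with power 80.7% by the normal approximation (78.1% for a t-test). Then 16/0.80 = 20, and 4 × 20 = 80. The stated sizes reproduce, and they rest on one active TENS arm against one placebo arm.

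**2. What the Framework contrasts cover.** Write P for Placebo TENS alone, T for TENS, E for PE+Placebo TENS and ET for PE+TENS.

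| Simple effect | Contrast | Planned? |
|---|---|---|
| TENS without education | T − P | yes |
| TENS with education | ET − E | yes |
| Education without TENS | E − P | yes |
| Education with TENS | ET − T | yes |

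The unplanned quantities are combinations of these:

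- TENS main effect = ½[(T − P) + (ET − E)]
- Education main effect = ½[(E − P) + (ET − T)]
- Interaction = (ET − E) − (T − P), which in Table 3 terms is (ET − P) − (T − P) − (E − P)

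Unadjusted point estimates therefore follow from the planned tables by arithmetic. Adjusted CIs do not, because the Table 3 contrasts share the placebo arm and their CIs cannot simply be combined.

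**3. Precision with 16 per arm, unadjusted.**

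| Quantity | Patients | SE | 95% CI half-width |
|---|---|---|---|
| Contrast of two arms | 32 | √(2/16) = 0.354 | 2.042 × 0.354 = 0.72 (own variance, 30 df); 2.000 × 0.354 = 0.71 (four-arm pooled variance, 60 df) |
| Factor effect, 32 v 32 | 64 | √(2/32) = 0.250 | 2.00 × 0.250 = 0.50 |
| Interaction | 64 | √(4/16) = 0.500 | 2.00 × 0.500 = 1.00 |

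If all 80 contribute (20 per arm), the half-widths are 0.64 (own variance), 0.445 and 0.89.

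Protocol 8.7 equates 1.0 SD with 169 m (TENS pilot) or 322 m (SEDRIC pilot). On that reading the factor half-width is 0.50 × 169 = 85 m or 0.50 × 322 = 161 m. For a contrast of two arms it is 0.72 × 169 = 122 m or 0.72 × 322 = 232 m.

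The documents give no correlation between baseline and follow-up ACD, so no adjusted width is stated. Baseline adjustment would scale all three by about the same factor and leave their ratios unchanged.

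**4. Limits of the interaction estimate.** For a true interaction of 0.5 SD, 0.5/0.500 = 1.0 standard error, so power is about Φ(1.0 − 1.96) = 17%. An interaction I places the TENS main effect I/2 away from each simple TENS effect. As an estimate of the simple effect, the main effect has the smaller mean squared error only while 2/32 + (I/2)² < 2/16, that is, while I < 0.50 SD.

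**The case against.** The strongest defence is that the plan already answers its stated question. All four simple effects are there, they match the aim of studying TENS with and without education, and the sample size is built on one of them. With point estimates derivable from the tables, and unadjusted CIs too if SDs of change and numbers analysed are shown, the only real gap is a pre-specified adjusted interval. A main effect is also a different quantity from the simple effect used for sizing. The SAP background says that the combination is untested, so additivity cannot be presumed, and this trial cannot verify it. Both documents put feasibility ahead of clinical differences, and the 10% eligibility and participation thresholds do not depend on these estimates.

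Most of this stands. It limits the importance of the point but does not supply the missing estimates. The shells do not say whether their SDs are of change or of values at each visit, so even unadjusted intervals may not be recoverable.

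Three stronger readings are tempting, and the documents do not support them:

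- *The arm-by-arm analysis is wrong, or the trial is mis-sized.* The contrasts are valid, and 16/20/80 reproduces on the contrast that the protocol names.
- *The effect of each treatment in the presence of the other is unplanned.* The Framework plans both comparisons. The footnote makes only their tabulation optional.
- *The factor effect is more precise from the same patients.* It is narrower because it uses 64 patients, where a contrast of two arms uses 32.

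**Conclusion.** The point holds as a cheap improvement to a valid plan. Neither document pre-specifies a TENS main effect, an education main effect or their interaction with a baseline-adjusted 95% CI. At the planned size a factor effect would have a half-width of 0.50 SD, against 0.71 to 0.72 SD for a contrast of two arms. The interaction, at 1.00 SD, can be estimated but not tested usefully. These figures assume equal arms, a common SD, 16 evaluable per arm and no baseline adjustment. At 3 months they would be wider, because only patients recruited in the first eight months are followed and their number is not stated. The non-superiority label is mainly a wording defect: the comparisons are planned, but nothing says what they are to show.

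**What to change.** Keep the planned arm contrasts, and leave protocol 8.7 unchanged. In the SAP:

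1. In the ANCOVA already planned for ACD, include baseline ACD, the stratification factors (gender, age, ABPI, in the form used at randomisation), TENS (active or placebo) and education (yes or no), with patients analysed as randomised. Apply it at 6 weeks and, for the follow-up subset, at 3 months.
2. Take both main effects with 95% CIs from the model without the product term. Take the interaction and its CI from the model with it.
3. Always report the main effects beside the interaction and the four simple effects. Do not use the interaction as a gatekeeping test, and say that the trial cannot rule out a material interaction.
4. State that the ANCOVA gives the effect estimates and CIs, and that the rank tests in Section 6 are supportive.
5. Replace the non-superiority wording with the difference and 95% CI for PE+TENS against each component, and make these entries in Tables 3 and 4 mandatory.

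The cost is SAP wording and two table shells, with no extra patients, visits or data. The downside is that a main effect averages over the other factor: with an interaction of 0.5 SD it would lie 0.25 SD from each simple effect. Item 3 is there for that reason.
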